## 10.2 Statistical analyses and methods

Demographics, and underlying conditions will be described by means and standard deviation for continuous variables, by median and interquartile range for ordinal or count variables, and by frequencies and percentages for categorical variables. Endpoints will be described and compared between treatment and usual standard of care groups using cross-tabulation tables and Fisher's Exact test for categorical variables, t-test for normally distributed continuous variables and Wilcoxon non-parametric test for non-normally distributed continuous or ordinal variables.

Safety variables such as fever will be considered in three different formats:

1. As ordinal, representing various levels of severity of the symptom. For instance, fever will be described as "none", "mild", "moderate", or "severe".
2. As binary, considering only the presence vs. the absence of the symptom.
3. As binary, considering the most serious expression of the symptom. For instance by grouping "moderate" and "severe" together.

Separate analyses for time periods of 0-3, 4-7, and 8-10 days will be conducted. For each of these time periods the most severe report of the AE for each participant will be counted.

Adverse Events and Serious Adverse Events will be considered in two ways: presence of any event and presence of any event related to the treatment.

Symptoms will be assessed as a repeated measure using GEE modelling.

Survival will be analyzed using a Kaplan-Meier curve and Cox-proportional hazard modeling with 2 week and 1 month survival rates determined.

Viral clearance will be analyzed as binary variables for detection (presence) or non-detection (absence) as well as continuous variables where applicable (e.g. quantitative RT-PCR measurements).

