## 1. Introduction

### 1.1 Background on Ebola Virus Infection

Clinical Ebola hemorrhagic fever is characterized by onset of fever, headache, myalgia, fatigue and gastrointestinal distress, 2-21 days post exposure to virus. Immune responses play a critical role in Ebola virus (EBOV) pathogenesis: infection is associated with an early loss of lymphocytes and down-regulation of interferon production and actions. There is subsequent dysregulation of coagulation, leading to clinically important hemorrhage in a minority of patients. The genus *ebolavirus* includes 5 different viruses: Sudan virus, Tai Forest virus, EBOV, Reston virus and Bundibugyo virus. EBOV has the highest fatality rate – 57-90%. Data from human infections with EBOV are limited, but the evidence from previous outbreaks suggests that the innate immune response is predictive of outcome. Specifically, an early and transient pro-inflammatory cytokine response, including IFN- $\alpha$ , is associated with survival, yet a sustained and increasing pro-inflammatory cytokine response, with dendritic cell infection that abrogates the IFN response, is associated with death (1, 2). Notably, in the absence of a robust innate immune response, including IFN- $\alpha$  activation of dendritic cells, the adaptive immune response (B and T cell activation) is severely impaired, leading to failure of control of viral replication and poor outcome.

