### **4. Hypothesis and Trial Objectives**

The study hypothesis is that IFN  $\beta$ -1a therapy will reduce viral load in Ebola-infected subjects, that IFN  $\beta$ -1a is safe to use in these individuals, and that the complications associated with EBOV infection can be prevented with IFN  $\beta$ -1a as a consequence of inhibiting viral replication.

The primary objective of this pilot study is to evaluate the effectiveness of IFN  $\beta$ -1a on viremia in peripheral blood of Ebola-infected subjects

The secondary objective is to evaluate the safety of IFN  $\beta$ -1a in Ebola-infected subjects

The tertiary objective is to determine whether IFN  $\beta$ -1a can prevent Ebola virus disease progression and/or on resolution of disease

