### 8.4 Evaluation of Safety

Safety will be assessed by comparing the occurrence of SAEs and of clinically important adverse events (moderate and severe) attributable to the intervention. Safety monitoring for this interventional study will involve collection of data with direct comparison between IFN  $\beta$ -1a-treated patients and those not receiving IFN  $\beta$ -1a.

Study stopping rules:

- A patient dies during therapy as a result of an SAE assessed as related to the investigational product.

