### 9.2 Secondary

**Safety:** Occurrence and severity of adverse event; time to onset, duration (number of days), severity, and seriousness of solicited and non-solicited injection site reactions and systemic adverse events occurring up to 7 days after the last injection. Occurrence, nature, time to onset relative to the first IFN  $\beta$ -1a dose, duration, severity, relationship to injection of SAEs throughout the trial.

- The frequency of clinically important (moderate or severe) adverse events will be compared between the groups
- The frequency of serious adverse events will be compared between the groups.

Parameters to look for adverse events will be solicited such as local injection site erythema and swelling, fever, heart rate, blood pressure, and rash.

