#### **16. Analysis of Final Data**

The initial results of the pilot trial will determine if it should be extended (extension to 100 participants per this protocol) and whether a larger multicenter study will be appropriate. Determining factors will be safety and, if possible with the small sample size, a trend toward efficacy when compared to the standard of care regimen. In addition, the effect of the treatment regimen on viral detection will be examined.

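### The safety hypothesis is assessed with a test of no difference and no interval, so a non-significant result at 30-50 treated patients cannot support the conclusion that IFN beta-1a is safe

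*Protocol*

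**What the plan says.** Section 4 includes in the study hypothesis that the drug "is safe to use in these individuals". The protocol gives no definition of safe, no tolerable excess and no acceptable rate.

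Section 8.4 sets out how this is judged: "Safety will be assessed by comparing the occurrence of SAEs and of clinically important adverse events (moderate and severe) attributable to the intervention". Section 9.2 repeats it as a secondary endpoint: "The frequency of serious adverse events will be compared between the groups". The groups are IFN-treated patients and patients who did not receive IFN. Section 5 describes the latter as retrospectively collected and matched, without giving their number or a matching ratio.

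For categorical endpoints, Section 10.2 names the method: "Endpoints will be described and compared between treatment and usual standard of care groups using cross-tabulation tables and Fisher's Exact test for categorical variables". It adds that adverse events are analysed as presence or absence and also with moderate and severe grouped together, so both safety frequencies fall under that test. No significance level, sidedness or confidence interval is given.

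Section 16 uses the result to decide on extension to 100 participants and on a larger multicentre study: "Determining factors will be safety and, if possible with the small sample size", a trend toward efficacy. The small-sample caveat is attached to efficacy only. Section 10.1 explains that 30-50 patients were chosen for feasibility.

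**The concern.** The hypothesis is that there is no unacceptable excess of harm. The named method tests whether a difference can be demonstrated. A significant excess would count against safety, but a non-significant result says only that the data could not separate the groups, and small groups often cannot. Without an interval, the reader cannot see how large an excess remains compatible with the data.

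This matters because safety feeds the decision to expose more patients, and Section 8.1 itself raises the possibility that treatment worsens the disease. Harm of that kind is hard to recognise case by case: Section 8.2 accepts that drug effects and symptoms of the infection may be difficult to tell apart. The group comparison is therefore the main place where an excess not attributed to the drug would appear.

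**Working it through.** The plan states no power, effect size or margin, so it has no figure to reproduce. The check asks how often the named test would stay non-significant when there is a real excess, and how wide the interval would be.

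**Inputs from the protocol**
- Treated patients: 30-50 (Sections 5 and 10.1).
- Test: Fisher's exact (Section 10.2).
- Fatal events are SAEs (Section 8.3), and Section 1.1 quotes 57-90% fatality for this virus. This suggests a background SAE rate of 57% or more.

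**Inputs assumed, because the protocol does not give them**
- Two-sided 5% level.
- One control per treated patient, with two per treated patient as a variant.
- Background SAE rate of 57-70%, with other values as sensitivity checks.
- A 20-point excess, chosen only for illustration.

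**Probability of a non-significant result**

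With n1 treated at rate p1 and n0 controls at rate p0 (X and Y being the event counts):

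miss = 1 − Σx Σy P(X = x | n1, p1) · P(Y = y | n0, p0) · 1[Fisher p(x, y) ≤ 0.05]

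This was enumerated exactly over both binomial distributions.

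| Control vs IFN SAE rate | 30 treated, 1:1 | 50 treated, 1:1 | 30 treated, 2:1 | 50 treated, 2:1 |
|---|---|---|---|---|
| 57% vs 77% | 71.9% | 51.0% | 58.4% | 33.4% |
| 60% vs 80% | 70.2% | 48.5% | 57.0% | 31.6% |
| 70% vs 90% | 62.8% | 36.0% | 43.8% | 18.6% |

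**Sensitivity (1:1 controls)**
- Lower backgrounds of 10-40%: 63-74% with 30 treated, 36-54% with 50.
- Very high background, 79% vs 99%: 47% with 30, 10% with 50.
- One-sided 5% level, backgrounds of 60% and 70%: 58% and 51% with 30; 36% and 25% with 50.

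**Scale**

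For 80% power against a 20-point excess (normal approximation with continuity correction, 1:1), about 96 per group are needed at 57% vs 77%, and 72 per group at 70% vs 90%.

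**What an interval would show**

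Suppose both groups show an SAE rate of 57%. The Wald 95% half-width for the difference is 1.96 × √(2 × 0.57 × 0.43 / n).
- n = 30 per group: 1.96 × √(0.4902 / 30) = 1.96 × 0.1278 = 0.251, so the upper limit is about +25 points.
- n = 50 per group: 1.96 × √(0.4902 / 50) = 1.96 × 0.0990 = 0.194, so the upper limit is about +19 points.

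Even a perfectly balanced result would leave an excess of about 20-25 points not ruled out. A Fisher p-value of 1 would not reveal that.

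**The case against.** A reader might infer that a harmful drug will usually be passed as safe. The documents do not support that. No section turns a p-value above 0.05 into a finding of safety: Section 16 names safety as a determining factor without a test criterion, and Section 10.2 speaks of description as well as comparison. Nor is usually borne out by the figures, since with 50 treated the miss rate is about one half or less over most of the range considered.

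Further objections, and what stands of each:

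- **The miss rates rest on assumptions.** This stands. The level, control ratio, background rate and effect size are not in the protocol, and 2:1 matching lowers the rates materially. Because suspected cases can be enrolled, 57% is not a firm floor either. The figures must be read as conditional.
- **A high background does not by itself hide an excess.** This stands. For a fixed 20-point excess the test gains power as the background rises above about 60%.
- **Fisher's test is not the only analysis.** This stands. Section 10.2 also gives the Wilcoxon test for ordinal severity, and Kaplan-Meier and Cox analyses for survival. None of these supplies an interval for the excess in SAE or moderate/severe adverse-event frequency.
- **There are other safeguards.** This stands: staggered dosing of the first ten patients (Section 2.3.2), causality assessment of every event (Section 8.3) and a stopping rule on a related death (Section 8.4). They work through case-level judgement and do not measure a group excess.
- **This is a feasibility pilot, so low power is no error.** This also stands, and the point is not a request for more patients. A size chosen for feasibility is a reason not to frame safety as a hypothesis to be settled by a difference test.
- **Bias may run the other way.** Retrospective charts may under-record events in controls, and the wording in Section 8.4 on events attributable to the intervention cannot apply to untreated patients. Both could inflate an apparent excess. That makes the p-value harder to interpret; it does not turn non-significance into evidence of safety.

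Interval reporting is often left to a statistical analysis plan. Here, however, the protocol has itself fixed the hypothesis, the test and the use of the result, and the three do not fit together.

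**Conclusion.** The mismatch is real. Section 4 hypothesises the absence of unacceptable harm, Section 10.2 names a test of no difference without an interval, and Section 16 relies on the safety result. Non-significance in that test cannot support the hypothesis.

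Under a two-sided 5% level, 1:1 controls and a background SAE rate of 57-70%, a 20-point excess would go undetected in about 63-72% of trials with 30 treated and 36-51% with 50 treated. With 2:1 controls the ranges are about 44-58% and 19-33%. These figures show why non-significance must not be read as safety. They do not predict what the investigators would conclude.

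**What to change.** - **Sections 10.2 and 16:** base the safety judgement on the between-group risk difference with its 95% confidence interval for SAEs, deaths and moderate/severe adverse events. Fisher's test may stay as a description.
- **Same sections:** state that a non-significant Fisher test will not be read as evidence of safety.
- **Section 4:** restate the safety hypothesis as an aim to estimate the excess risk and report its upper confidence limit.

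A margin fixed in advance by the sponsor is optional and not part of the required change. In a feasibility pilot with retrospective controls, its value is open to debate.

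The cost is wording, plus intervals from data already to be collected. The downside is small: the pilot may be able to say only that an excess of about 20-25 points has not been ruled out, which is all that groups of this size can show in any case.

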**Synopsis**

Product provided by:	BiogenIdec Inc.
Investigational Product/ Drug Product:	Interferon beta-1a (IFN $\beta$ -1a)
Title of the Study:	A Pilot Study to Evaluate the Safety and Efficacy of IFN $\beta$ -1a in the Treatment of Patients Presenting with Ebola Virus Illness.
Development phase:	I/II
Sponsor-Investigator:	[name] [name]
Collaborator:	[name]
Planned Study Period:	January/February 2015 to April/May 2015
Primary Objective:	To evaluate the effectiveness of IFN $\beta$ -1a on viremia in peripheral blood
Primary Endpoint:	Viral load reduction/clearance: Reduction and/or clearance in copies/mL of viral RNA from day 1 to day 14 and, if applicable, 30 days after the last dose
Secondary Objectives:	To evaluate the safety of IFN $\beta$ -1a in the treatment of Ebola virus disease
Secondary Endpoints	
Occurrence and severity of adverse event; time to onset from the initial dose, duration (number of days), severity, and seriousness of solicited and non-solicited injection site reactions and systemic adverse events occurring up to 7 days after the last injection. Occurrence, nature, time to onset from the initial dose, duration, severity, relationship to injection of SAEs throughout the trial, and up to 30 days post-treatment.
 
The frequency of clinically important (moderate or severe) adverse events will be compared between the IFN <math>\beta</math>-1a treatment group and the group receiving usual standard of care.
 
The frequency of serious adverse events will be compared between the groups.

Tertiary Objectives	
To evaluate the effect of IFN <math>\beta</math>-1a therapy on preventing Ebola virus disease progression and/or on resolution of disease.
 
To assess effects on disease symptoms and survival.

Tertiary Endpoints	
Clinical improvement will be evaluated by comparing the following parameters between the groups:
 
Days in treatment centre
 
Days of symptom manifestation: hemorrhage (as IFN <math>\beta</math>-1a may cause fever, myalgia, sore throat, headache, nausea, vomiting, and diarrhea similar to that associated with ebola virus infection, these adverse events will be recorded but not used in the analysis of efficacy).

	Death – all causes for study duration

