### 6.5 Follow-up

Collection from daily recordings will be undertaken either prospectively or retrospectively to assess adverse event and efficacy of therapy from day 1 (1st day of treatment) to day 10 and then weekly while admitted to the treatment centre and then 30 days post last dose. For patients for whom therapy is discontinued prior to day 10, assessments will follow the same schedule to allow comparison of disease course.

The following will be recorded, as permitted, starting immediately prior to the onset of administration of IFN  $\beta$ -1a, then on a daily basis whilst the patient is in the treatment centre:

- Temperature; fever will be defined as a temperature  $\geq 38$  °C.
- Concurrent illness symptoms: chills, myalgia, cough, sore throat, nausea, vomiting, diarrhea, hemaorrhage.
- Adverse events will be recorded per protocol. Medication history at baseline and daily will be recorded.
  - Blood samples:
    - 20 cc of Blood for virologic measurement (if feasible).
    - A convalescent serum (10 cc tiger top tube) will be obtained at 1 month (when possible).
  - Survival

Of note, it is expected that there will be missing data points for study participants depending on the clinical care data available in the medical chart and residual blood samples available for testing.

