### 8.3 Adverse Event Definitions and Reporting

Adverse Event (AE): is any untoward medical occurrence in a patient or clinical investigation participant administered a product. It does not necessarily have to have a causal relationship with this treatment. An AE can therefore be any unfavorable and unintended sign (including an abnormal laboratory finding, for example), symptom or disease temporally associated with the use of a medicinal product, whether or not considered related to the medicinal product.

All adverse events will be recorded and transcribed into the CRF. Solicited AEs and non-solicited AEs will be collected daily for the first four days and then every 2-3 days during therapy, or whenever reported by patients. SAEs will be collected while on study medication and for 30 days after administration of the last dose.

**Serious Adverse Event (SAE):** is any adverse event that:

- is fatal
- is life-threatening
- results in persistent or significant disability/incapacity
- requires initial hospitalization or prolongation of existing hospitalization
- causes congenital anomalies or birth defects

The term "life-threatening" refers to an event in which the patient was at risk of death at the time of the event. It does not refer to an event, which hypothetically might have caused death, if it were more severe. All deaths occurring while on protocol therapy or within 30 days of the last dose, should be reported (see below).

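### Non-serious adverse events count to 7 days after the last injection, but the two collection schedules conflict, neither secures that window after discharge, and the period analyses end at day 10

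*Protocol*

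**What the plan says.** **Endpoint.** The Synopsis defines the secondary safety endpoint by "solicited and non-solicited injection site reactions and systemic adverse events occurring up to 7 days after the last injection", and Section 9.2 uses the same limit.

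**Collection, Section 8.3.** Solicited and non-solicited events are "collected daily for the first four days and then every 2-3 days during therapy, or whenever reported by patients". Only serious events are carried further: "SAEs will be collected while on study medication and for 30 days after administration of the last dose".

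**Collection, Section 6.5.** Adverse events and efficacy are assessed from day 1 (the first treatment day) "to day 10 and then weekly while admitted to the treatment centre and then 30 days post last dose". A list of items that includes adverse events is recorded before the first dose and "then on a daily basis whilst the patient is in the treatment centre". Patients who stop before day 10 stay on this schedule.

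**Discharge.** Section 6.3 allows 7 to 10 days of treatment and expects it to end at discharge or about 48 hours before. Section 6.2 offers patients discharged before day 10 a visit one month after treatment start, if possible.

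**Analysis.** Section 10.2 states: "Separate analyses for time periods of 0-3, 4-7, and 8-10 days will be conducted". The Synopsis has the same periods and compares endpoints between baseline and day 10. Section 10.2 also analyses the presence of any event, and of any treatment-related event, without naming a day limit.

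**The concern.** The endpoint, the collection rule and the analysis periods describe three different stretches of time. A site that follows Section 8.3 stops scheduled recording of non-serious events with the last dose, a week before the endpoint closes. A site that follows Section 6.5 continues during admission, but has nothing scheduled between discharge and the 30-day contact.

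Safety is the secondary objective, and Section 16 makes it a determining factor in whether the pilot is extended. The post-injection days are not idle ones: Section 7.2 reports that response markers stay raised for at least 4 days after a dose and that the elimination half-life ranges up to 54 hours. The endpoint also asks for onset, duration and severity. An event still present at the last dose would have its duration cut short if recording stopped there.

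**Working it through.** The protocol states no figure for this point, so there is nothing to reproduce. The check is a day count and a side-by-side reading.

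**Inputs.** First dose on day 1 (6.5). Ten planned daily doses, or seven as the minimum after rapid recovery (6.3). Endpoint closes 7 days after the last injection (Synopsis, 9.2). Last analysis period closes at day 10 (10.2).

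**Step 1: days outside every analysis period.** Endpoint end = day of last dose + 7. Days outside = endpoint end − 10, or zero if negative.

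| First dose numbered | Doses | Last dose | Endpoint ends | Days outside | Share of endpoint window |
|---|---|---|---|---|---|
| Day 1 | 10 | day 10 | 10 + 7 = day 17 | 17 − 10 = 7 | 7/17 = 41% |
| Day 1 | 7 | day 7 | 7 + 7 = day 14 | 14 − 10 = 4 | 4/14 = 29% |
| Day 1 | 3 | day 3 | 3 + 7 = day 10 | 0 | 0/10 = 0% |
| Day 0 | 10 | day 9 | 9 + 7 = day 16 | 16 − 10 = 6 | 6/17 = 35% |
| Day 0 | 7 | day 6 | 6 + 7 = day 13 | 13 − 10 = 3 | 3/14 = 21% |

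The day-0 rows are there because the first period starts at 0. The conclusion for full courses does not depend on the numbering.

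**Step 2: post-injection days with no scheduled contact.** If treatment stops 0 to 2 days before discharge (6.3), the patient is in the centre for about 0 to 2 of the 7 days. That leaves 7 − 2 = 5 to 7 − 0 = 7 days unobserved, even under Section 6.5. Contact at 30 days after the last dose comes 30 − 7 = 23 days after the window has closed.

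**Step 3: the two collection rules side by side.**

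| | Section 8.3 | Section 6.5 |
|---|---|---|
| During therapy | Daily for four days, then every 2-3 days | Daily |
| After therapy, still admitted | Spontaneous reports only | Continues (daily in one sentence, weekly after day 10 in another) |
| After discharge, days 1-7 after the last injection | Spontaneous reports only | Nothing scheduled |
| 30 days after last dose | Serious events | Assessment |

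The rules differ both on therapy and after it. The adverse-event item in the Section 6.5 list refers back to the protocol, so it does not settle which rule governs.

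**Step 4: day 0.** Section 6.5 starts recording just before the first dose. If that record is day 0, the 0-3 period can take a pre-dose Ebola symptom as a patient's worst report. This is a smaller matter of labelling.

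**The case against.** The strongest reply is that the protocol does provide for events after treatment. Section 6.5 continues assessment during admission and again at 30 days. Section 8.3 accepts reports from patients at any time. Section 12 follows withdrawn participants for safety off therapy. The three periods are called separate analyses, and the any-event analysis beside them has no day limit. The protocol also accepts missing data openly, given the outbreak. All of this stands, and it limits the point.

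A reader might infer three stronger conclusions, which the document does not support:

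- *That post-treatment events are not captured at all, or are analysed only to day 10.* Section 6.5 and the any-event analysis contradict this. The day-10 limit belongs to the period analyses and the Synopsis comparison.
- *That serious events after day 10 are lost.* They are explicitly collected to 30 days after the last dose, so their days beyond day 10 are not a collection gap.
- *That the treatment will necessarily look safer than it is.* Uncollected events can only lower the treated group's own count. The comparison group is a retrospective chart series with its own gaps, so the direction of any bias in the between-group difference cannot be fixed from the document.

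The 41% and 29% are likewise shares of days, not of events.

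The reply does not close the gap after discharge, and it does not remove the conflict between Sections 8.3 and 6.5. A statistical analysis plan, which is not available here, could add a period or settle day numbering, but it could not recover observations that sites were never told to make.

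**Conclusion.** The point holds in limited form. Sections 8.3 and 6.5 conflict on how non-serious events are collected, and neither secures the 7-day window for patients discharged around the end of treatment. For a full ten-dose course all 7 post-treatment days fall outside every analysis period; for seven doses 4 of 7 do. With day-0 numbering these become 6 and 3. Patients still admitted and patients who stop early are wholly or partly covered, and after three doses the whole window lies within day 10.

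The figure of about 5 to 7 days without scheduled contact assumes that discharge follows the expectation in Section 6.3. Patients who stay longer have fewer such days. How many events would be missed cannot be estimated from the document. The matter should be corrected, since the stated endpoint cannot be relied on under Section 8.3 as written and the correction is cheap.

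**What to change.** 1. **Sections 8.3, 6.5 and 9.2:** give one schedule for solicited and non-solicited events, running to 7 days after the last injection while the patient is in the centre. For discharged patients, ask about that window at the 30-day or one-month contact already planned, and mark such data as recalled.
2. **Section 10.2 and Synopsis:** state that the any-event analysis covers the full endpoint window, and bring the Synopsis comparison into line.
3. **Section 10.2 and Synopsis:** add a period after day 10, for example days 11-17, counted from the same index day in treated and comparison patients. A period defined only by the last dose would not exist for untreated comparators.
4. **Day numbering:** keep pre-dose findings as baseline and start the first post-dose period at day 1.

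**Cost:** revised wording and a few more case report form days. Data for discharged patients will be recall-based or missing, and charts of retrospective comparators may not reach day 17. Both limits should be acknowledged when results are reported.

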**A. Case definitions for Suspect or Probable Ebola virus infection:****Clinical Criteria for Ebola virus infection**

- One or more clinical findings of illness associated with a history of at least one of the following symptoms:
  - Temperature of  $>38^{\circ}\text{C}$  ( $100.4^{\circ}\text{F}$ ) and/or
  - Myalgia and/or
  - Fatigue and/or
  - Headache and/or
  - Sore throat and/or
  - Nausea or vomiting
  - Diarrhea
  - Hemorrhage

**Confirmed Case:** Ebola virus disease which meets the clinical criteria with laboratory confirmation for the presence of EBOV by PCR (or qRT-PCR) for the presence of viral genome and/or acute/convalescent serology.

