**5.3 Inclusion Criteria**

Only potential patients fulfilling all of the following criteria are eligible for enrolment in this interventional trial.

1. Able to provide informed consent. Substitute decision maker may provide informed consent in cases where the patient is ill and unable to provide informed consent.
2. Aged  $\geq 18$  years and  $< 70$  years of age on the day of inclusion.
3. Is admitted to the treatment centre.
4. Suspect, probable or confirmed EBOV infection as defined above.
5. Symptoms onset  $< 4$  days
6. Is able to comply with all trial procedures.

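### Section 10.2 counts symptoms already present at entry as safety events in both groups, which dilutes the between-group safety contrast, most directly in days 0-3

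*Protocol*

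**What the plan says.** Section 10.2 of the protocol opens its safety analysis with "Safety variables such as fever will be considered in three different formats": an ordinal grade from none to severe, a binary version ("As binary, considering only the presence vs. the absence of the symptom") and a second binary version that groups moderate with severe. It then sets three windows (days 0-3, 4-7 and 8-10) and the counting rule "For each of these time periods the most severe report of the AE for each participant will be counted". The synopsis repeats the scheme, with AE in place of symptom in the three formats.

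The case definition in section 5.2 asks for "One or more clinical findings of illness associated with a history of at least one of the following symptoms". The list is fever, myalgia, fatigue, headache, sore throat, nausea or vomiting, diarrhea and hemorrhage. A confirmed case is "Ebola virus disease which meets the clinical criteria with laboratory confirmation for the presence of EBOV", so it must meet the same clinical criteria. Section 5.3 makes this the entry condition: "Suspect, probable or confirmed EBOV infection as defined above".

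Section 6.5 plans daily recording of temperature and symptoms "starting immediately prior to the onset of administration of IFN" β-1a, and calls the first day of treatment day 1. The synopsis lists among the safety endpoints "time to onset from the initial dose, duration (number of days), severity".

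**The concern.** The symptoms that bring a patient into the trial overlap with those scored as safety variables. Section 10.2 does not refer the windowed count to the pre-dose record that section 6.5 plans. A fever present on admission that is still there after the first dose is scored as present, at its worst grade, in the first window. So is the same fever in an untreated comparator. Part of each group's event rate then reflects Ebola at entry, which reduces the room for a drug effect to show.

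Safety is the secondary objective. Section 16 also names it as a determining factor for extending the pilot to 100 participants and for a larger study. A count that leans towards no difference is a poor basis for that decision. Time to onset from the first dose also has no sensible value for a symptom that began before that dose.

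**Working it through.** **1. Is there a baseline condition anywhere on the windowed count?**
- Section 10.2: none in the three formats or in the counting rule.
- Section 8.3: an adverse event is any untoward occurrence in a participant given a product. It need not be new or worse than before.
- Synopsis, statistical methods: a baseline-to-day-10 comparison for the treatment group. It does not reach the day 0-3 count and has no untreated arm.
- Synopsis, tertiary endpoints: the symptom overlap is recognised, but the remedy is to keep these symptoms out of efficacy. They are still recorded as adverse events.

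**2. What can fall in days 0-3?** Day 0 is not defined, and two readings are open.
- Study days: with day 1 as the first treatment day, day 0 precedes treatment and pre-dose observations fall inside the window.
- Elapsed days since first dose: the window starts at dosing, but an entry symptom that persists is still counted. Section 8.1 expects the disease to progress for the first 24-72 hours, so persistence in this window is likely.

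The problem exists under both readings. Under the first it is larger.

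**3. Size of the dilution.** The plan has no figure to reproduce: section 10.1 bases 30-50 patients on feasibility and gives no alpha, power or effect size. The illustration uses:
- p, the rate of new fever without and with the drug: 9% and 20%, from the multiple sclerosis figures in section 8.2;
- b, the share febrile at entry and still scored present: not given in the protocol, assumed 0.5 to 0.9 and equal in both groups.

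Observed rate per group = b + (1 − b)p, so the difference is (1 − b) × (20 − 9) points.

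| b | Untreated | Treated | Difference (points) |
|---|---|---|---|
| 0 | 9.0% | 20.0% | 11.0 |
| 0.5 | 54.5% | 60.0% | 5.5 |
| 0.7 | 72.7% | 76.0% | 3.3 |
| 0.9 | 90.9% | 92.0% | 1.1 |

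For flu-like symptoms (29% against 49% in the same section), 20 points become 10, 6 and 2.

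**4. Power, for scale.** Assume 30 or 50 per group, two-sided 0.05 and a normal approximation. For fever, power is 0.22 or 0.34 at b = 0, and 0.05 or 0.06 at b = 0.7. Fisher's exact test, which the plan names, gives less: 0.12 or 0.24, and 0.03 or 0.04.

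**5. After the change.** Among patients without fever at entry the full 11 points return. At b = 0.7 that leaves 30 × 0.3 = 9 or 50 × 0.3 = 15 per group, with power 0.10 or 0.13 by the normal approximation. The denominator matters: over all patients, new fever would be 0.3 × 9% = 2.7% against 0.3 × 20% = 6.0%, again 3.3 points.

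**The case against.** The strongest reply is that a treatment-emergent definition and day-window conventions usually sit in an analysis plan, which is not shown. The adverse event definition in section 8.3 and the measurement of onset from the first dose also suggest that events were meant to begin after dosing. This carries some weight. But section 10.2 states a counting rule outright, and it scores the symptom. The section 8.3 definition is tied to receiving a product, so it cannot screen entry symptoms in the untreated comparators.

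The protocol also has safeguards. Every adverse event is assessed for causality, section 8.4 looks at events attributable to the intervention, and treatment-related events are analysed separately. However, untreated patients cannot have treatment-related events, so these give no between-group contrast, and section 8.2 concedes that attribution may be difficult. Other replies stand: the ordinal grade can show worsening, symptoms are also modelled as repeated measures by GEE, and injection-site reactions and rash are unaffected.

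The rates in the illustration come from intramuscular use in multiple sclerosis, not daily subcutaneous use in Ebola, and b is assumed. They show the mechanism and do not forecast this trial.

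A reader might infer more than the documents support:
- That every patient enters with fever. The criteria ask for a history of any one listed symptom.
- That day 0 must be the pre-dose record. It is undefined, and section 6.2 labels the pre-treatment baseline day 1 of hospitalization.
- That an imbalance in presenting symptoms will pass as a drug effect. The synopsis says comparators presented with similar symptoms. Section 5 does not list symptoms among its matching factors, so imbalance is possible but not shown.

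**Conclusion.** The point holds as a dilution of the between-group safety contrast. As written, presence and worst-grade counts mix persisting entry symptoms with drug effects, most directly in days 0-3. The difference shrinks by the factor (1 − b): in the fever illustration, from 11 points to between 5.5 and 1.1 for b between 0.5 and 0.9. This rests on an assumed b that is equal in the two groups, on entry symptoms being scored as present in the window, and on borrowed multiple sclerosis rates.

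A reader might infer that any effect of the drug would be hidden. The documents do not support that: the contrast is reduced and not erased, and several planned analyses keep some information. Nor would the change make this a well-powered safety comparison. It is worth making because the data it needs are already planned and the result feeds the extension decision.

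**What to change.** In section 10.2 and the synopsis:
- For the between-group safety counts, count a symptom only if it is new or at least one grade worse than the last record before the first dose. For comparators, use the admission or matched index-day record.
- Start the first window after the first dose, or after the index time for comparators, and define the day numbering.
- Compute time to onset only for these events.
- Give the number at risk (for new symptoms, patients free of the symptom at entry) as the denominator.
- Tabulate entry symptoms as baseline data, and keep the all-symptom count as a supplementary table.

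The cost is mainly wording, since section 6.5 already plans the pre-dose record. Four downsides should be stated. A symptom already at the top grade cannot worsen, so its persistence appears only in the supplementary table. Baseline investigations depend on resources and missing data are expected (sections 5, 6.2 and 6.5), so patients with no pre-dose record need one default applied identically in both groups; otherwise the rule could itself create a difference. Ebola progression after dosing still counts as an event. The pilot remains too small for a well-powered safety comparison.
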